## **Lay summary**

### **Introduction**

There are approximately 1.5 million major operations carried out in the NHS every year. As the population ages, and surgical technique becomes more advanced, more patients are undergoing operations which carry a high risk of complications. Currently, doctors predict this risk by asking patients about their history of medical problems and how these impact on how active they are able to be. Investigations such as a heart scan or breathing tests can give further information. If an operation is very high risk, a patient may undergo cardiopulmonary exercise testing (CPET) where the patient rides an exercise bike to maximum effort (exhaustion) whilst their heart and lung function is monitored. This gives the doctor specific numbers which can be discussed with the patient about the risk of complications after surgery. By using a portable heart rate monitor placed on the skin we aim to produce a new measure of a patient's fitness for surgery which can be easily performed at clinic without needing to exercise to maximum effort (submaximal). This measure looks at how quickly heart rate slows again after submaximal exercise, called heart rate recovery (HRR).

### **Aim**

To assess whether HRR is a valid measure of a patient's risk of post-operative complications.

### **Method**

With their consent, patients undergoing intermediate/high risk non-cardiac surgery will be asked routine questions and blood tests will be taken. Patients will then be asked to perform a HRR assessment. To do this, a small external device will be placed on the patient's chest and their heart rate recorded. This will be done sitting at rest and performing a step test until approximately two-thirds of their predicted maximum heart rate is reached. The patient will step on and off a low box for a further minute and then rest for five minutes. Additionally, some patients will undergo pre-operative CPET as part of their routine care. After the operation, blood tests indicating whether the patient's heart has been under strain will be taken on days one and two and the presence of post-operative complications will be recorded. Patients will also complete questionnaires to describe the quality of their recovery and quality of life. Data regarding their length of hospital stay and, if applicable in rare cases, death will also be collected. This data will be analysed to see how well HRR predicts post-operative complications and how well it agrees with the predictive measures doctors currently use.

### **Expected outcome and implications**

HRR tests will predict post-operative complications in intermediate/high risk surgical patients and will prove a valid measure compared to current practice. HRR could be used as part of a doctor's toolkit to predict the operative risk of surgical patients. Future studies will investigate whether HRR can be improved with exercise, so could be targeted to improve patients' fitness for surgery. Patients identified as high risk could be offered interventions to reduce their risk and therefore improve patient outcomes after surgery.

## 1. **Background and rationale**

### 1.1 **Introduction**

There are approximately 1.5 million major operations performed in the UK annually, with the majority of these surgeries carrying an intermediate (1-5%) or high (>5%) mortality risk. The number of operations performed annually is increasing concurrent with an increase in population age and therefore the prevalence of co-morbidities. Despite this, surgical mortality is reducing. In 2017 all major NHS surgery was found to have a 30-day mortality of 1.1%. A planned sub-analysis of the ENIGMA-II study demonstrated that 15.7% of patients with increased peri-operative cardiovascular risk undergoing non-cardiac surgery developed a major post-operative complication. This was associated with a 1-year disability-free survival of 87.5% and a 1 year mortality of 7.4%. As well as increasing the risk of mortality and further morbidity, post-operative complications have been shown to cause detriment to an individual's quality of life. Post-operative complications also affect wider society by adding a financial burden on limited NHS resources, and reducing the ability of patients and their families to contribute towards the economy. One of the main ways to mitigate post-operative complications is via effective pre-operative risk stratification.

### 1.2 **Pre-operative risk assessment**

Pre-operative risk assessment is primarily based on patients' functional capacity. This encompasses an assessment of how co-morbidity and physiological fitness impacts on patients' daily life and indicates the level of cardiopulmonary reserve available for undergoing the physiological insult of surgery. Current modalities for pre-operative risk stratification range from subjective assessments and validated physiological scoring systems such as the Surgical Outcome Risk Tool (SORT), to measurement of biomarkers such as brain natriuretic peptide (BNP), and to cardiopulmonary exercise testing (CPET), an objective measure of cardiopulmonary function. Subjective assessment of patients' functional capacity conducted via pre-operative interview has been shown to be unreliable. Validated scoring systems combine multiple risk indices to stratify post-operative risk. Activity scales such as the Duke Activity Index Score (DASI) however still rely on the patient's subjective view of their ability to perform daily tasks, whilst physiology scores such as P-POSSUM do not include functional domains. Biomarkers are increasingly proposed as part of peri-operative risk stratification. Brain natriuretic peptide (BNP) is a hormone released by cardiac myocytes in response to stress. BNP and corresponding N-terminal proBNP (NT-proBNP) are recommended by the European Society of Cardiology for cardiac risk stratification in high risk patients. The gold-standard exercise test for measuring functional capacity is CPET. CPET comprises incremental workload increases during cycle ergometry until exhaustion and peak oxygen consumption ( $VO_{2\text{peak}}$ ) is reached. Analysis of measured variables including oxygen consumption at anaerobic threshold and  $VO_{2\text{peak}}$  determine the patient's risk threshold for post-operative morbidity and mortality. Unfortunately, a proportion of patients are unable to perform effective CPET, for example due to arthritis or failure to reach maximal exertion. CPET is also resource-intensive and its availability varies extensively. Submaximal exercise tests are advocated as predictive tests because they are better tolerated for patients and are less resource-intensive than maximal exercise testing. Defined cut-offs for risk however are limited, as measurements are effort-dependent i.e. HRR may be relative to the peak heart rate reached during the submaximal test. Different methods of HRR analysis can take this into account, and analysis of the whole HRR curve may give further information. Previous work by our group has identified novel objective submaximal heart rate recovery (HRR) analyses to account for effort by HRR and utilising the whole HRR curve profile. As an intermediary (enabling high risk patients to be triaged to formal CPET) or alternative objective measure of physiological fitness we suggest HRR measured after submaximal exertional effort as a simple, lower-cost alternative.

### 1.3 Exercise physiology and functional capacity

During exercise, cardiac output increases linearly to meet the metabolic demands of contracting skeletal muscle. Heart rate (HR) increases and there is an associated rise in systolic blood pressure and stroke volume to increase oxygen delivery to working muscles in order to match oxygen consumption ( $VO_2$ , the product of cardiac output and arterio-venous oxygen content difference). This HR increase occurs primarily due to initial withdrawal of vagal stimulation, with sympathetic activation at moderate work rates increasing as exercise intensity increases, although the extent of this autonomic “imbalance” is debated. At exercise cessation, heart rate initially drops rapidly due to reactivation of the parasympathetic system followed by a slower reduction due to withdrawal of sympathetic stimulation. Vagal modulation therefore is a very important component in the attainment of oxygen delivery, consumption and recovery during exercise.

Training (repetitive exercise at increasing intensities) improves the  $VO_{2\max}$ , the maximum rate at which oxygen is used during dynamic exercise. This is via adaptation of the cardiorespiratory and skeletomuscular system in a variety of ways including increased stroke volume and reduced resting heart rate, and improved skeletal muscle oxygen utilisation. Resting heart rate is indicative of vagal activity as the vagus reduces the intrinsic rate of cardiac pacemaker cells. It has long been assumed that vagal activity is a marker of aerobic fitness but recent evidence also suggests that cardiac vagal activity also determines the ability to exercise. Therefore, measures of vagal tone can indicate both the aerobic capacity of an individual, but also their potential to respond to exercise and training.

In Anaesthesia, the term functional capacity is used to describe the ability of the body to increase and maintain tissue oxygen delivery and consumption in response to the physiological stress and increased oxygen demand that surgery places on the body. Although the mechanisms are different to exercise, the surgical stress response results in an increase in  $VO_2$ , primarily via entering a catabolic state which can continue for several days post-operatively. Inability to compensate for this increased oxygen demand increases the risk of post-operative complications including delayed wound healing, impaired immune function and organ failure. Therefore, an individual with a higher functional capacity is likely to be able to maintain oxygen delivery to the tissues under surgical stress better than an unfit individual. This forms the fundamental pretext underlining the majority of pre-operative assessment and risk stratification for patients. On this basis, a patient’s capacity to exercise is a surrogate marker for how their body will cope with the increased oxygen demand of surgery. It follows that vagal tone can be used as a measure of functional capacity in surgical patients.

### 1.4 Markers of vagal parasympathetic activity

There are three relatively simple in-vivo methods to indicate vagal activity measured via electrocardiograph: heart rate variability (HRV), resting heart rate and heart rate recovery. Heart rate variability describes the oscillation between R-R intervals. There are many indices incorporated within HRV measurement but overall, high HRV indicates high vagal tone. HRV however, is dependent on resting heart rate and respiration, and recent evidence suggests that it may not be a reliable measure. A low resting heart rate indicates high vagal activity as the vagus inhibits activity of the cardiac pacemaker cells in the sino-atrial node which have an intrinsic rate of approximately 100-110bpm. There is also some evidence that in trained athletes, a low resting heart rate also reflects a reduced intrinsic pacemaker cell rate. In patients with subclinical cardiac failure a higher resting heart rate is associated with increased post-operative mortality, and in healthy individuals associated with an increased risk of developing cardiac failure over a 15 year period. Although reflective of vagal tone, the

parameters of resting heart rate which increase peri-operative risk have not been defined. Heart rate recovery presents a measure combining both heart rate evaluation and exercise testing.

### **1.5 Heart rate recovery**

HRR after exercise is mediated by rapid re-activation of the parasympathetic nervous system^23 and has been shown to be independent of resting heart rate and respiration, but correlates with other markers of vagal tone. Greater initial HRR is considered to indicate greater aerobic fitness (Figure 1). HRR has been described as a prognostic marker in heart failure, after non-cardiac surgery and in healthy individuals. The majority of studies investigating the prognostic application of HRR measure HRR1 (reduction in HR one minute after exercise cessation after maximal exercise). HRR1 ≤12bpm after symptom-limited maximal exercise is a strong predictor of mortality in patients with coronary artery disease. A study by Ha et al investigated HRR1 after six minute walk test (submaximal) and found that post-operative cardiopulmonary complications were increased in patients undergoing lung resection with HRR1<12bpm. HRR1 however is effort-dependent, so may not be the most appropriate measure for submaximal exercise testing. HRR after two minutes (HRR2) ≤42bpm after exercise cessation predicted all-cause mortality in healthy individuals. Further analyses of submaximal HRR as a peri-operative risk measure are absent, so it is an area requiring further investigation.

### **1.6 Previous HRR work**

Previous volunteer studies by our group have developed novel methods for HRR assessment utilising all the data contained within the HRR curve, including non-linear mixed-effects modelling and determination of the area under the curve (Figure 1), and have demonstrated their reproducibility following submaximal exercise across differing workloads and exercise modalities.

The exercise protocol for the submaximal test used in this investigation (detailed below) is based on these previous study findings. Specifically, this prior work reveals that in a healthy population, resting heart rate is approximately 40% predicted maximum heart rate (HRmax). Reproducibility across differing exercise modalities was demonstrated. Participants walked on a flat surface, performed a ramped protocol on an exercise bike, and repeatedly stepped on and off a low box. During the step test, participants reached a median (IQR) of 64%(62-72%) predicted HRmax. All of our previous work has examined HRR over a recovery time of six minutes. However, during the six minutes heart rate does not return to baseline, even when exercising at low levels (e.g. 20% predicted maximum power). In general, the heart rate curve plateaus after approximately four minutes after cessation of exercise (Figure 1).

The natural next step of our group's work therefore is the validation of effort-corrected submaximal HRR in a clinical population (Table 1).

[figure not shown]

Figure 1 Graphs demonstrating HRR curves after cessation of exercise. a) typical curve of fitter participant with high  $HRR_1$  and smaller AUC, incorporating lower resting HR. b) typical curve of less fit participant for comparison. Red dashed line = baseline HR. Yellow line = non-linear mixed-effects modelling curve from which rate constant can be obtained. AUC can be effort-corrected by dividing AUC by effort ratio (cessation HR/age-corrected maximal HR).

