#### **5.4.2 Step test**

Prior to the exercise, the patients' age-predicted maximum heart rate will be calculated:

$$\text{Age predicted HR}_{\text{max}} = (208 - 0.7 \times \text{age})$$

The aim of the test will be for the patient to repetitively step onto and off a low box until they reach 60% predicted  $\text{HR}_{\text{max}}$  +/- 5% or the point of subjective limitation. Participants will be encouraged throughout to place alternate feet onto the top of the box, stand erect at the top of the box and place both feet fully on the ground at the end of the stepping "cycle". Standard phrases of encouragement will be used in a neutral tone. Once the HR is approximately 60% predicted  $\text{HR}_{\text{max}}$ , the patients will maintain the effort for a further minute. At the end of the minute, patients will sit and rest. Heart rate will continue to be monitored for a further 5 minutes. A modified Borg score will be assessed at the beginning and end of the test as an indication of perceived workload. The step test also allows an estimate of work done to be calculated:

$$\text{Work done (J)} = \text{mass (kg)} \times \text{height of step (m)} \times 9.8 \text{ (gravity)} \times \text{total number of step cycles}$$

During the test, patients will be asked not to speak as this has been demonstrated to raise heart rate.

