# **7. Statistical Considerations**

Our group has developed novel indices for measuring heart rate recovery including area under the curve and non-linear mixed effects modelling. This study is part of a higher degree programme (MD by research; [name]) which will encompass statistical methodology as an iterative process. The primary method of measuring HRR will be effort-corrected area under the curve (EC-AUC) but our other methods will also be examined. A formal statistical analysis plan will be written and agreed between the principal investigator (CH) and chief investigator (BS) prior to any data analysis.

All statistical analysis will be carried out using R-studio.

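### Dividing the area by the effort ratio does not make the primary index, EC-AUC, independent of effort, and the direction of the remaining effect depends on a lower limit the text does not state

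*Combined protocol and SAP*

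**What the plan says.** Section 1.2 gives the reason for correcting: "measurements are effort-dependent i.e. HRR may be relative to the peak heart rate reached during the submaximal test". Section 1.6 names validation of an effort-corrected index in patients as the group's next step. Section 7 makes it primary: "The primary method of measuring HRR will be effort-corrected area under the curve (EC-AUC"), adding that the group's other methods will also be examined and that a formal analysis plan will be agreed before any analysis.

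The only formula is in the Figure 1 caption: "AUC can be effort-corrected by dividing AUC by effort ratio (cessation HR/age-corrected maximal HR"). The text does not say whether the area is measured down to zero or down to baseline heart rate. The caption describes the fitter participant's curve as having a "smaller AUC, incorporating lower resting HR", which points towards area to zero.

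Section 5.4.2 lets effort differ between patients. The target is 60% of predicted HRmax, +/- "5% or the point of subjective limitation", and no lower limit is given for a limited test. After reaching target, "the patients will maintain the effort for a further minute", so cessation heart rate can drift from the target. In the group's earlier step test, "participants reached a median (IQR) of 64%(62-72%) predicted" HRmax (section 1.6). The protocol states no adjustment for cessation heart rate and no rule for analysing symptom-limited tests.

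**The concern.** A ratio removes effort only if the numerator is proportional to the denominator. A recovery area is not proportional to cessation heart rate, because resting heart rate enters the area whichever lower limit is used. Two patients of the same age and resting rate, with identical recovery, can therefore receive different scores because they stopped at different heart rates.

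Patients who stop for limitation may well carry higher surgical risk. Part of the AUROC for EC-AUC could then reflect inability to step to target (area to zero), or a real recovery signal could be diluted or reversed (area above baseline). What is at stake is the attribution of any prediction to effort-corrected recovery, which is the property the study sets out to validate.

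**Working it through.** The protocol gives no figure for how EC-AUC varies with effort, so there is none to reproduce. Its sample size of 90 does reproduce (Hanley-McNeil variance, two-sided: 22 + 68) and is not affected.

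**Inputs**
- HRmax = 208 - 0.7 x age (section 5.4.2).
- Recovery window T = 5 min (section 5.4.2).
- Resting rate R = 0.40 of HRmax: "resting heart rate is approximately 40% predicted maximum heart rate" (section 1.6, healthy volunteers).
- Cessation rate P = 0.55 to 0.65 of HRmax, reading the 5% as percentage points.
- Assumed, not in the documents: mono-exponential recovery, HR(t) = R + (P - R)exp(-t/tau), with tau = 1 min, doubled to 2 min for comparison.

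**Algebra.** Let A = tau(1 - exp(-T/tau)), which is always less than T.
- Area to zero = RT + (P - R)A. Dividing by P/HRmax gives EC-AUC = HRmax x [A + R(T - A)/P], which always falls as P rises.
- Area above baseline = (P - R)A. Dividing gives EC-AUC = HRmax x A(1 - R/P), which always rises with P.

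Neither form is free of P.

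**Numbers** (P and R as fractions of HRmax; areas in HRmax x min; A = 0.9933 at tau 1 and 1.8358 at tau 2)

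| Stop, tau | To zero, uncorrected | To zero, EC-AUC | Above baseline, uncorrected | Above baseline, EC-AUC |
|---|---|---|---|---|
| 55%, 1 min | 2.149 | 3.907 | 0.149 | 0.271 |
| 60%, 1 min | 2.199 | 3.664 | 0.199 | 0.331 |
| 65%, 1 min | 2.248 | 3.459 | 0.248 | 0.382 |
| 60%, 2 min | 2.367 | 3.945 | 0.367 | 0.612 |

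- To zero: the uncorrected area changes by 2.248/2.149 = +4.6% from 55% to 65%. EC-AUC differs by 3.907/3.459 = 13.0% in the opposite direction. Doubling tau moves EC-AUC by 3.945/3.664 = 7.7%. The correction enlarges the effort dependence and reverses its sign.
- Above baseline: the uncorrected area changes by 66.7% and EC-AUC by 0.382/0.271 = 41%. Doubling tau moves EC-AUC by 0.612/0.331 = 85%. The correction helps but leaves much of the effect.

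**Rank reversal, area to zero, age 70** (HRmax 208 - 49 = 159). With tau 1 min stopped at 55%: 159 x 3.907 = 621. With tau 2 min stopped at 65%: 159 x (1.8358 + 0.40 x 3.1642/0.65) = 601. The faster recoverer has the larger area and so looks less fit.

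**Sensitivity, area to zero.** At R = 40% and starting tau 0.67 to 1.33 min, the 55-65% range moves EC-AUC by 11.6-14.5%, against 6.0-8.5% for doubling tau. The two break even at resting rates of about 28%, 33% and 36% of HRmax for starting tau 0.67, 1.0 and 1.33 min. At R = 35% with tau 1.33 doubled, the comparison narrowly fails (11.0% against 11.5%). If the 5% is relative (57-63%), the EC-AUC values are 3.805 and 3.537, a 7.6% difference, about equal to doubling tau.

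**Share of rank, illustrative.** Assume tau median 1.2 min (log-SD 0.35), cessation rate uniform over 55-65% and resting rate SD 3% of HRmax. Area-to-zero EC-AUC then has Spearman correlation 0.47 with tau, -0.47 with cessation rate and 0.70 with resting rate.

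**Effect on AUROC, illustrative.** Simulate recovery speed unrelated to injury, with age N(70, 8), resting rate N(70, 9), tau median 1.5 min (log-SD 0.3) and 24.5% injury overall. Let 10-30% of patients stop at 45-55% of HRmax with 2-3 times the injury risk, and the others stop uniformly over 55-65%. AUROC is 0.53-0.61 (area to zero) or 0.40-0.47 (above baseline), where recovery itself carries 0.50.

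**The case against.** Several points on the other side stand. The lower limit may be evident from Figure 1 or the cited source, neither of which was available here. Section 7 promises other methods, which include the mixed-effects rate constant; under the model above that constant is already free of effort. The analysis plan is still to be written. Section 1.6 reports reproducibility across workloads, although without figures and in volunteers, so it neither confirms nor refutes the calculation. None of this sets a rule for when EC-AUC and another index disagree.

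The AUROC figures are fragile. The documents give no share of limited patients and no risk ratio. Patients must be able to walk unaided, and volunteers mostly exceeded 60%. In the simulation about 18% of limited patients had a cessation rate at or below rest. With 20-30% limited, removing them lowers the area-to-zero range from 0.55-0.61 to 0.54-0.59. All values are well short of the design alternative of 0.7.

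A reader might infer three stronger claims that the documents do not support:
- That EC-AUC always moves more with stopping point than with a doubling of recovery time. This fails above baseline over 55-65% (41% against 85%) and, for area to zero, turns on resting rate and tau.
- That patients are ranked simply by where they stopped. Resting rate and recovery speed also drive rank, in shares that depend on spreads not given.
- That the study could not show prediction at all. A discriminating EC-AUC would still be evidence of predictive validity under section 7.2; what weakens is attribution to recovery.

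**Conclusion.** The point holds in a bounded form. That the division leaves effort in EC-AUC follows from the caption's formula under exponential recovery to rest, whichever lower limit is used; the sign of the remaining effect depends on that limit. The sizes rest on an assumed curve shape and time constant and on a volunteer resting rate: about 13% over 55-65% for area to zero, where the correction makes matters worse than the raw 4.6%, and 41% above baseline. Stopping point is one substantial contributor to rank among three. The possible AUROC bias is modest and conditional on limited patients being both common and at higher risk. The matter should be settled in the analysis plan before any data are examined.

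**What to change.** In section 7 and the analysis plan:
- State the AUC's lower limit and the 5-minute window.
- Keep EC-AUC as primary. Report beside it the AUROC of the effort ratio alone and of one pre-specified, less effort-dependent index: either the mixed-effects rate constant already planned, or area above baseline divided by (cessation minus baseline heart rate), computed only above a stated minimum rise.
- Plot each index against cessation heart rate.
- Record on the CRF whether each test ended at target or at limitation.
- Attribute prediction to effort-corrected recovery only if the effort ratio does not explain it.

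The cost is analysis-plan wording and one CRF field; baseline rate, cessation rate and the recovery trace are already recorded. The downside is that the ratio index is noisy when the rise is small, which is where limited patients lie. It is also only approximately effort-free, because section 1.6 reports that heart rate had not returned to baseline even after six minutes.
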